6.4.4. Safety endpoints

1. Device safety
The incidence of adverse events in general and by seriousness, severity and association to the device.
2. Treatment tolerability
The percent of subjects who fail to complete the study because of device-related adverse events.

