	
patient consumes at least one dose of any medication (OTC or prescribed) for acute treatment of headache or migraine.
 
[Endpoints 2-6 below relate to the pre-emptive follow-up phase]
 
2. Percentage of patients who treat for the first treatment in the pre-emptive phase, during a prodrome, when they are pain free, and remain pain free during the following 2 hours after the treatment, without use of acute medication.3. Percentage of patients who treat for the first treatment in the pre-emptive phase, during the prodrome, when they are pain free, and remain pain free during the following 24 hours after the treatment, without use of acute medication.4. Percentage of patients who treat for the first treatment in the pre-emptive phase, during the prodrome, when they are pain free, and remain either pain free or with mild pain during the following 24 hours after the treatment without use of acute medication.5. Mean change in the percentage of prodromes which were followed by a headache within 24 hours from baseline to the end of the pre-emptive follow-up phase.6. Mean change in the average number of moderate/severe headache days per month in the pre-emptive phase compared to the 4-week baseline phase. 
[Endpoint 7 relate to Health Economics analysis]
 
7. Differences between active and sham groups in reduction of the following events from baseline (weeks 1-4) to the last 4 weeks of treatment phase (weeks 9-12): (a) Absenteeism, (b) Presenteeism, (c) Healthcare provider appointments, (d) ED/ER visits, (e) Brain MRI/CT scans 
[Endpoint 8 relate to migraine prediction analysis]
 
8. Feasibility of a migraine prediction algorithm: Analysis of the daily information provided by the participants during the baseline period (weeks 1-4) for the purpose of predicting their migraine days
Safety endpoints	
1. The incidence of adverse events in general and by seriousness, severity and association to the device.2. Treatment tolerability (by electronic patient report).

theranica	QMS document Nerivio TCH-008 Clinical Study Protocol	Doc ID: TEC0250 Revision #: 3.0 Page: 13 of 58
------------------	--	--

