After the enrollment visit, participants will undergo a 4-week baseline phase aimed to collect headache days, medication use, migraine symptoms, and further assess eligibility. Participants will use the app daily to record headache with time of onset, migraine symptoms and medication use. To ensure compliance, the app will send daily reminders/notifications in a pre-specified time in the evening chosen by the participant, but the questionnaire will be available throughout the day. The daily reports will be transferred by the application to the electronic data capture (EDC) system, where they will be collected and registered.

Qualification to enter into the treatment phase: Participants who complete the diary in at least 22 out of the 28 days during the baseline phase (80%), have between 6 to 24 headache days during the 28-day baseline period, at least 4 of their headache days during the baseline phase fulfill the ICHD-3 criteria for migraine (migraine without aura [code 1.1; C and D], or with aura [code 1.2; B and C], or probable migraine, or headaches requiring the use of migraine-specific medications such as triptans, gepants or ergot derivatives) will continue to the treatment phase. Participants who fail these criteria will be excluded from the study and considered screen failure.

Second visit-

Device training: Eligible participants who successfully complete the baseline phase will be randomized in a 1:1 ratio into one of the two groups: either active (treatment with Nerivio active device) or sham group (treatment with Nerivio sham device). During this visit, participants will receive general instructions on study procedures, device mode of operation and warnings/precautions. After the training, patients will be instructed to use the device at home every other day.

The site personnel will be required to document the training session in the CRF. If the visit is conducted remotely, the devices will be shipped/mailed to the participant beforehand, with clear instructions not to open the device before the training.

	QMS document Nerivio TCH-008 Clinical Study Protocol	Doc ID: TEC0250 Revision #: 3.0 Page: 34 of 58
---	--	--

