Before the first device use, the participants will watch a short instructional video that includes how to pair the device, finding the optimal individual stimulation intensity level (perceptible but not painful, just below the pain threshold), and instruction to use the device every other day for 45 minutes and to complete a daily questionnaire.

Treatment phase:

During this 8-week phase, participants will be instructed to use the device every other day for 45 minutes. Participants will also be instructed to continue completing a daily diary with information on their headaches with time of onset, migraine symptoms and medication use, as performed in the baseline phase. Participants will be instructed to use the device with an intensity level that is perceptible but not painful. Adverse events will be reported throughout this phase of the study directly to the site staff and recorded in the CRF.

Participants can treat their migraine and headaches with their usual acute treatments. (Nerivio will not be used for acute treatment to avoid bias between the groups).

Blinding will be assessed at the end of the treatment phase when participants will be asked of their presumed group assignment (active, sham, do not know).

Third visit-

Transition to the follow-up phase (open label):

During the visit, participants will complete the following questionnaires:

1. Patient assessment of treatment group during the treatment phase
2. HIT questionnaire regarding weeks 9-12
3. MSQ regarding weeks 9-12

At the end of the 8-week treatment phase, participants from both arms (active and sham) may continue to an open-label follow-up phase in which they will receive an active Nerivio device to use during the follow-up phase.

Participants who meet the following conditions will be offered to enter the **pre-emptive follow-up phase**:

- Between 6 to 16 headache days during the baseline phase.
- Participants experience at least one prodromal symptom, within 24 hours prior to the onset of their migraine headache, in at least half of their migraine attacks during the baseline phase.
- Participants completed the daily questionnaires in at least 70% of the days during the treatment phase
- Treated every other day on at least 24 and no more than 32 days during the 56 days of the treatment phase.

theranica	QMS document Nerivio TCH-008 Clinical Study Protocol	Doc ID: TEC0250 Revision #: 3.0 Page: 35 of 58
------------------	--	--

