7.2.4. Safety endpoints

The safety endpoints of adverse events and tolerability will be assessed by review of all safety parameters, including adverse events.

The incidence of treatment related adverse events will be assessed as a function of severity and association to the device. The time of resolution of the adverse events and need for treatment will also be analysed.

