7.6.4. Safety analysis

Safety and tolerability will be assessed on the ITT analysis set by reviewing of all safety parameters, including adverse events. Serious adverse events, device-related SAEs, adverse events (by type and overall), device-related AE, adverse device reactions and device malfunction rates will be documented. Treatment tolerability, the number and percent of subjects who fail to complete the study and the number and percent of

	QMS document Nerivio TCH-008 Clinical Study Protocol	Doc ID: TEC0250 Revision #: 3.0 Page: 45 of 58
---	--	--

subjects who fail to complete the study because of adverse events will be presented. Time to withdrawal will also be assessed and presented by Kaplan-Meier curves.

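### Treatment tolerability, one of two safety endpoints, is stated differently in four places, and non-completion is not tied to the blinded phase

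*Combined protocol and SAP*

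**What the plan says.** The synopsis and Section 6.4.4 each list two safety endpoints: adverse events and treatment tolerability. Tolerability is then described as follows.

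- Synopsis, Safety endpoints: "Treatment tolerability (by electronic patient report", with no variable, item or time point.
- Section 6.4.4: "The percent of subjects who fail to complete the study because of device-related adverse events".
- Section 7.2.4: "The safety endpoints of adverse events and tolerability will be assessed by review of all safety parameters, including adverse events".
- Section 7.6.4: "Treatment tolerability, the number and percent of subjects who fail to complete the study and the number and percent of" and, continuing over the page break, "subjects who fail to complete the study because of adverse events will be presented". Causality is not mentioned in the withdrawal rows.

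On data sources, Section 6.3 has participants in the treatment phase "continue completing a daily diary with information on their headaches with time of onset, migraine symptoms and medication use". Adverse events go to site staff and the CRF, not through the app.

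On timing, Section 6.3.1 gives a study duration of up to 16 weeks per participant. Weeks 13 to 16 are an optional open-label phase in which both arms receive an active device. Section 6.5 locks the database once the last patient has finished the treatment phase.

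**The concern.** A reader who follows Section 6.4.4 counts one set of participants. A reader who follows Section 7.6.4 counts another, and a reader of the synopsis looks for a questionnaire that the plan does not describe. The choice could then be made after the data are seen.

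The second problem concerns the comparison between arms. Sections 6.4.4 and 7.6.4 both count failure to complete the study as a whole. If that runs to week 16, a participant randomised to sham who stops an active device in week 14 because of an adverse event is a tolerability failure in the sham arm. This would make the active device look better tolerated relative to sham than it is. Section 5.1 sets the goal as fewer migraine headache days with a favorable safety profile maintained, so a declared safety endpoint should have one reading.

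**Working it through.** No planned figure attaches to this endpoint, so there is none to reproduce. The check sets the texts side by side.

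| Place | Who counts | Cause required | Window |
|---|---|---|---|
| Synopsis | not stated (a data source only) | not stated | not stated |
| 6.4.4 | non-completers | device-related adverse event | the study |
| 7.2.4 | not stated (general review) | not stated | not stated |
| 7.6.4, first row | non-completers | any reason | the study |
| 7.6.4, second row | non-completers | any adverse event | the study |

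**Step 1: does the analysis section deliver the declared endpoint?** Section 7.6.4 lists device-related adverse events as counts, but names no row for withdrawal because of them. The 6.4.4 quantity is a subset of its second row, so the two figures differ whenever someone leaves because of an adverse event judged unrelated.

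**Step 2: is an electronic source described?** The baseline diary is given as "Participants will use the app daily to record headache with time of onset, migraine symptoms and medication use", and the treatment-phase diary has the same content. The third-visit questionnaires are the group guess, HIT and MSQ. The pre-emptive questionnaires cover headache, prodrome and medication. Section 6.6 rules out direct questions on treatment perception before the treatment phase ends. The one other candidate is an optional final-visit questionnaire on experience with the device. Its content and medium are not stated, and it follows the open-label phase.

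**Step 3: what window applies?** 4 baseline + 8 blinded + 4 open-label = 16 weeks, which matches Section 6.3.1. Non-completion of the study can therefore include the open-label weeks. Under Section 6.5, the last participants may still be in those weeks when the database is locked, so their 16-week status may be unknown.

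**Step 4: which withdrawals count?** Section 6.1.3 lists inability to tolerate treatment, within difficulties with the product, as a reason separate from a serious adverse event. A participant recorded under it falls outside 6.4.4 unless a device-related adverse event is also recorded.

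**Step 5: what size?** Section 4.3.2 reports no adverse-event withdrawals in the pivotal study, and Section 4.2.3 none in TCH-005. Taking the adverse-event denominators of those studies (126 per arm; 42), the exact two-sided 95% upper limit for zero events is 1 − 0.025^(1/n):

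- n = 126: 1 − 0.025^(1/126) = 2.9%
- n = 42: 1 − 0.025^(1/42) = 8.4%

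Both studies tested acute use, not treatment every other day for 8 weeks, so they are only a rough guide.

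One reclassified participant moves an arm's rate by 1/117 = 0.85 percentage points at the arm size in Section 7.4. If all 375 were randomised, the shift would be 1/187.5 = 0.53 points. How many would be reclassified cannot be derived from the documents.

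**The case against.** The strongest reply is that this is loose wording in a descriptive summary. The synopsis names a source, not a variable. Section 7.6.4 can be read as a list in which tolerability is its own item, carried over from 6.4.4, with the two withdrawal rows added to it. Investigators grade device relationship for every adverse event (Section 12.1), so both counts come from the same CRF data. No test or success threshold attaches to tolerability. Much of this stands. Even so, on the list reading Section 7.6.4 leaves tolerability undefined, and the synopsis, 6.4.4 and 7.2.4 still differ.

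Four stronger readings are tempting, and the documents do not support them.

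- **The definitions contradict one another.** They do not in logic: the device-related count is nested in the any-cause count. They can give different results.
- **The earlier studies show a 2-to-10-fold gap.** Participants with any adverse event against device-related events were 9/99 v 1/99 (TCH-006), 10/45 v 1/45 (TCH-004) and 2/42 v 1 (TCH-005). These are adverse-event counts, not withdrawals, from open-label acute-use studies, one of them in adolescents. In TCH-005 both withdrawal versions would have been zero.
- **The electronic version cannot be produced.** The diary lists are not exhaustive. They omit headache severity and functional disability, which the endpoints in Sections 6.4.2 and 6.4.3 need. Section 9.1 keeps the case report forms and statistical analysis plan as separate documents. What can be said is that no tolerability item is described.
- **Declining open label makes someone a tolerability failure.** This could affect only the any-reason row, because that person did not leave because of an adverse event.

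**Conclusion.** The point holds as an inconsistency to be reconciled. A declared safety endpoint reads differently in four places, none is said to govern, and its completion window is open. The window matters most, because it can place events on the active device in the sham column.

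The size of the effect cannot be computed from the documents. Both adverse-event versions may be near zero, as in the two earlier studies, and the difference would then be small. The any-reason row could be much larger, since Section 7.4 anticipates about 35% discontinuation. That figure is applied to enrolled participants and may include losses before randomisation, so it is not an estimate of tolerability.

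The primary efficacy analysis is unaffected. The conclusion assumes that no separate document already fixes the definition.

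**What to change.** Use one definition in the synopsis and in Sections 6.4.4, 7.2.4 and 7.6.4: the percent in each randomised arm (ITT) who do not complete the 8-week double-blind phase because of a device-related adverse event. Show discontinuation in the same phase for any adverse event, and for any reason, as supportive rows.

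State how withdrawals recorded as inability to tolerate treatment (Section 6.1.3) are counted, so that none is lost because a reason code was used instead of an adverse-event form. Report open-label discontinuations separately, and say in Section 6.5 when those data are locked. Delete the electronic-report qualifier from the synopsis unless an existing item can be identified. No new diary question is needed.

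The cost is wording in a few sections and one or two extra summary rows. No new data are collected. The blinded-phase figure is complete when the last patient finishes treatment, which fits the lock already planned.

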6.5. Methods and timing of assessing and analysing variables

Once the last patient completes the treatment phase of the study and all the queries will be resolved, the database will be locked, cleaned, and exported for final statistical analysis. A study report will be issued following the final database lock.

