	
2. Uncontrolled epilepsy.3. History of use of opioids or barbiturates on more than 4 days a month in the last 6 months.4. Current participation in any other interventional clinical study5. Participants without basic cognitive and motor skills required for operating a smartphone.6. Pregnant or breastfeeding.7. Other significant pain, medical or psychological problems that in the opinion of the investigator may confound the study assessments.8. Prior experience with the Nerivio device.
Study Design	
A prospective, randomized, double blind, sham controlled, multicenter trial, conducted in three phases. The trial will consist of a screening/enrollment visit, followed by a 4-week (28 days) baseline phase. Eligible participants will enter an 8-week double-blind preventive treatment phase. Following the preventive treatment phase, patients will be offered to participate in a 4-week open label pre-emptive treatment phase or continue their prevention treatment with an active device, according to their eligibility.
 
Patients will complete an electronic diary throughout the study; this includes a daily evening report (completed regardless of whether the patient had a headache) and a treatment feedback during the follow up pre-emptive phase
 
Phase I – Baseline - 4 weeks (weeks 1 through 4):
 
Eligible participants will install the Nerivio app on their smartphones and will be instructed to record daily their migraine/headaches symptoms and medication use on the Nerivio app.
 
Transition to the treatment phase:
 
Participants who meet the following criteria in the baseline phase will be eligible to continue to the treatment phase:
 
• Complete the diary in at least 22 out of the 28 days during the baseline phase (80%)• Have between 6 to 24 headache days during the 28-day baseline period.• At least 4 of their headache days during the baseline phase fulfill the ICHD-3 criteria for migraine (migraine without aura [code 1.1; C and D] or with aura [code 1.2; B and C], or probable migraine, or headaches

requiring the use of migraine-specific medications including triptans, gepants or ergot derivatives)

Phase II - treatment phase (prevention) – 8 weeks (weeks 5 through 12):

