Participants who meet the baseline phase requirements will be randomized in a 1:1 ratio to active and sham groups. Participants will be instructed to complete a daily diary (in the Nerivio app) about their headaches, associated symptoms, and medication use. They will also be instructed to conduct a 45-minute treatment with Nerivio every other day.

Transition to the follow-up phase (open label):

At the end of the treatment phase, participants from both arms (active and sham) may continue to a follow-up phase in which they will receive an active device that can be used during this phase. The data of all participants will be used for safety analyses.

The data of participants from the baseline and treatment phases will be used to assess their eligibility to participate in the pre-emptive follow-up phase.

Participants eligible for the follow-up phase meet the following conditions:

- Between 6-16 headache days during the baseline phase.
- Participants experience prodrome symptoms within 24 hours prior to the onset of their migraine headache in at least half of their migraine attacks during the baseline phase.
- Participants completed the daily questionnaires in at least 70% of the days during the treatment phase.
- Treated every other day in at least 24 and less than 33 days during the 56 days of the treatment phase.

Phase III – Follow-up phase (open label) - 4 weeks (weeks 13 through 16):

All participants will receive an active Nerivio device to use during the follow-up phase. Participants who do not meet the above requirements will be able to enter into the safety follow-up and continue to use Nerivio every other day for the preventive treatment of migraine. They will be instructed to complete a daily diary as was done in the treatment phase.

	
Participants who meet the above requirements will enter the pre-emptive follow-up phase and be instructed to conduct a 45-minute device treatment within 60 minutes of prodrome symptom onset. Participants will be instructed to complete questionnaires regarding their headache, prodrome symptoms, and medication use at baseline (start of treatment), 2 hours post-treatment, and 24 hours post-treatment. In addition, participants will be instructed to continue to report the daily diary, as performed in the other phases of the study.

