6.4.3. Exploratory efficacy endpoints

1. Difference between treatment groups in the reduction in the mean number of acute headache/migraine medication days per month in the last 4 weeks of the treatment phase (weeks 9 through 12) compared to Baseline (weeks 1 through 4).

An acute headache/migraine medication day is a calendar day on which the patient consumes at least one dose of any medication (OTC or prescribed) for acute treatment of headache or migraine.

[Endpoints below relate to the pre-emptive follow-up phase]

2. Percentage of patients who treat for the first treatment in the pre-emptive phase, during a prodrome, when they are pain free, and remain pain free during the following 2 hours after the treatment, without use of acute medication.
3. Percentage of patients who treat for the first treatment in the pre-emptive phase, during the prodrome, when they are pain free, and remain pain free during the following 24 hours after the treatment, without use of acute medication.
4. Percentage of patients who treat for the first treatment in the pre-emptive phase, during the prodrome, when they are pain free, and remain either pain free or

	QMS document Nerivio TCH-008 Clinical Study Protocol	Doc ID: TEC0250 Revision #: 3.0 Page: 38 of 58
---	--	--

with mild pain during the following 24 hours after the treatment without use of acute medication.

5. Mean change in the percentage of prodromes which were followed by a headache within 24 hours from baseline to the end of the pre-emptive follow-up phase.
6. Mean change in the average number of moderate/severe headache days per month in the pre-emptive phase compared to the 4-week baseline phase.

[Endpoint below relate to Health Economics analysis]

7. Differences between active and sham groups in reduction in the means of the following events from baseline (weeks 1-4) to second month of treatment (weeks 9-12):
 - a. Absenteeism – number of missed work/school days
 - b. Presenteeism – number of work/school days with moderate/severe functional disability
 - c. Healthcare provider appointments
 - d. ED/ER visits
 - e. Brain MRI/CT scans
8. Feasibility of a migraine prediction algorithm:
Analysis of the daily information provided by the participants for the purpose of developing a migraine prediction algorithm.

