12.2. Reporting of AEs and SAEs

All adverse events will be recorded in appropriate adverse events case report form. The adverse events will be used for the safety assessment. An on-site visit to monitor the adverse event will be conducted if the principal investigator determines it is needed. These visits will be reported using designated case report forms. If during the last visit, an ongoing device-related AE is present, the participant will be monitored for approximately 2 weeks, until the AE resolves or a steady state is achieved.

The PI must report any SAE or SADE to the sponsor within 1 business day:

Theranica Bioelectronics

[name]

[contact]

Fax: [name]

Email: [contact]

The sponsor is responsible for reporting the adverse events to regulatory agencies, IRB/IECs, and investigators in accordance with all applicable global laws and regulations.

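### The final database lock is tied to the end of the treatment phase (week 12), although the tolerability endpoint, open-label safety data and exploratory endpoints 2-6 need data to week 16

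*Combined protocol and SAP*

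**What the plan says.** Section 6.5 gives the rule: "Once the last patient completes the treatment phase of the study and all the queries will be resolved, the database will be locked". The data are then exported for the final statistical analysis, and "A study report will be issued following the final database lock". Two other places mention a lock. Section 7.6.7.1 describes a soft lock for the interim analysis, and Section 6.7 foresees exports for the interim and final analyses. No separate lock or export is described for the follow-up phase.

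The treatment phase is a defined period. The Synopsis labels it "Phase II - treatment phase (prevention) – 8 weeks (weeks 5 through 12"), and a separate period follows it: "Phase III – Follow-up phase (open label) - 4 weeks (weeks 13 through 16"). Section 6.3 ends the study at a fourth visit after that period, and Section 6.3.1 gives a duration of up to 16 weeks per participant.

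Several planned outputs draw on weeks 13-16:
- **Exploratory endpoints 2-6** (Section 6.4.3), introduced with "Endpoints below relate to the pre-emptive follow-up phase".
- **Tolerability** (Section 6.4.4), defined as the percentage who do not complete the study because of device-related adverse events.
- **Non-completion counts and Kaplan-Meier time to withdrawal** (Section 7.6.4).
- **Open-label adverse events.** In the Synopsis paragraph on the move to follow-up: "The data of all participants will be used for safety analyses".
- **Device-related adverse events still ongoing at the last visit** (Section 12.2), for which "the participant will be monitored for approximately 2 weeks".

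**The concern.** The lock is tied to a milestone four weeks before the last participant can finish. Anyone still in follow-up at that moment has an incomplete record in the dataset used for the final report.

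The outputs are affected differently:
- **Tolerability.** This is a simple proportion. A participant still in week 14 at the lock has neither completed nor failed to complete the study, and the plan does not say how to count such a person.
- **Time to withdrawal.** Kaplan-Meier curves can censor these participants at the lock, so the loss is of information on the last weeks.
- **Open-label safety.** Sham participants first receive an active device in this phase. For those enrolled last, the cut-off could remove part or all of their active exposure.
- **Exploratory endpoints 5 and 6.** These compare baseline with the whole pre-emptive phase, so a partial phase gives a partial value.

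Safety is half of the stated objective in Section 5.1, so the final report should not rest on partial follow-up without saying so.

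**Working it through.** **Step 1. Reproduce the plan's timeline.** Inputs: baseline 4 weeks (Synopsis: "followed by a 4-week (28 days) baseline phase"), treatment 8 weeks, follow-up 4 weeks.

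4 + 8 + 4 = 16 weeks, which matches Section 6.3.1.

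**Step 2. Place the lock trigger on it.** End of treatment phase = 4 + 8 = week 12. If the lock came at that moment, the last participant would be missing:
- 4 of 16 study weeks: 4/16 = 25%
- 4 of 12 device-use weeks: 4/(8 + 4) = 33%

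**Step 3. Estimate how many participants are affected.** The documents give neither the accrual period nor the time needed to resolve queries, so both are assumptions here. Let L be the days from the last participant's week 12 to the lock, and D the accrual period in days (months × 30.44). With uniform accrual, and with everyone opting into follow-up:

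share incomplete = max(0, 28 − L) / D

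| Accrual | D (days) | L = 0 | L = 14 | L = 28 |
|---|---|---|---|---|
| 6 months | 182.6 | 28/182.6 = 15.3% | 14/182.6 = 7.7% | 0% |
| 12 months | 365.3 | 7.7% | 3.8% | 0% |
| 18 months | 547.9 | 5.1% | 2.6% | 0% |
| 24 months | 730.6 | 3.8% | 1.9% | 0% |

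For L = 0 this is about 36 to 9 of 234 participants, or 57 to 14 of 375, going from 6 to 24 months of accrual. Fewer are affected if some decline follow-up.

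**Step 4. Follow-up time lost.** An affected participant loses on average half of the remaining gap, so the share of follow-up person-days lost is (share incomplete) × ((28 − L)/2)/28. At 6 months and L = 0: 15.3% × 14/28 = 7.7%. At 24 months and L = 0: 3.8% × 14/28 = 1.9%. At 6 months and L = 14: 7.7% × 7/28 = 1.9%.

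**Step 5. Where the lock would have to sit.** The end of scheduled follow-up is 4 weeks after the present trigger. With about 2 weeks of monitoring for an ongoing device-related event, it is 4 + 2 = 6 weeks, before visit windows.

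**The case against.** The strongest reply is that the lock also waits for query resolution. If that takes four weeks or more, almost all scheduled follow-up is captured and little is lost. This stands as a limit on the size. It does not settle the point, because nothing in the plan makes the lock wait for follow-up to finish, and completeness would depend on how long queries happen to take.

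Second, follow-up is optional, endpoints 2-6 are exploratory and uncontrolled, and they come from a subset that meets four entry conditions. Endpoints 2-4 use only the first pre-emptive treatment, so a participant partway through may already have contributed. All of this is right, and it keeps the point minor. Reporting of serious events to the sponsor also does not depend on the lock.

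Third, the Synopsis sentence on safety data can be read as saying who is included, not for how long. That is fair, but the tolerability endpoint and endpoints 5-6 need the later weeks whichever reading is taken.

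Fourth, Section 9.1 lists a data management plan and a statistical analysis plan kept separately, and a staged lock may be described there. This cannot be checked here. It would still leave Section 6.5 stating a rule that needs correcting.

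Two stronger readings are tempting, and the documents do not support them:
- **A gap of over seven weeks for everyone.** A reader might add 28 days, the 10-day visit window in Section 6.3 and 14 days of monitoring to get 52 days. But the window is a maximum, and the monitoring applies only to a device-related event still ongoing at the last visit.
- **Locking before cleaning.** A reader might infer this from the word order in Section 6.5. But the same sentence has queries resolved before the lock, and Section 8.3 has the case report forms signed after cleaning and review.

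**Conclusion.** The point holds as a conflict within the protocol. The only lock defined for the final analysis is triggered at week 12 of the last participant, while several planned outputs run to week 16, or about two weeks longer for an ongoing device-related adverse event. The word final in Section 6.5 is adequately explained by contrast with the interim soft lock, and no later lock is defined.

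The consequence is limited. It falls on participants who opted into follow-up and are still in it at the lock. A reader might infer that the main efficacy result is at risk. It is not, because the primary and secondary endpoints end with weeks 9-12.

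The size cannot be derived from the documents. The upper bound of about 15% to 4% rests on uniform accrual over 6 to 24 months, an immediate lock and full uptake of follow-up. It halves with 14 days of query resolution and is near zero with 28 days or more. This is a minor point that is easily corrected.

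**What to change.** Amend Section 6.5 in one of two ways:

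1. **One lock.** Tie the final lock to the last participant's end of follow-up, including any monitoring of an ongoing device-related adverse event. The cost is a delay of about 4 to 6 weeks to all results.
2. **Two locks.** Lock the double-blind data after the last week-12 visit for the primary and secondary analyses. Make a final lock after the last Phase III visit and adverse event monitoring, for the complete safety analysis and exploratory endpoints 2-6. The cost is one additional lock, with no delay to the primary result.

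In either case, state which lock the study report uses. With two locks, also state that site staff and participants stay blinded to the Phase II allocation until the final lock, because open-label adverse events are still being reported and assessed in that interval.
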